3.4 OUTCOME MEASURES

3.4.1 Primary Outcome Measures

- Incidence, nature, and severity of adverse events and clinical laboratory abnormalities (graded according to the Division of Acquired Immunodeficiency Syndrome [DAIDS] Toxicity Grading Tables for Clinical Abnormalities) associated with the administration of MHAA4549A to patients with influenza A as measured by changes in vital signs, physical findings, *and* clinical laboratory results

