- Asymptomatic elevations of ALT, AST, and/or amylase without corresponding elevations of bilirubin have been shown to be increased during influenza A infection (Polakos et al. 2006; Yingying 2011).
- Influenza associated disease and/or complications of influenza

An IMC and SOC will monitor the incidence of the above-listed anticipated events during the study. An aggregate report of any clinically relevant imbalances that do not favor the test product will be submitted to health authorities.

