6.4 PRIMARY SAFETY ANALYSES

The safety analyses will include all randomized patients who received study drug, with patients grouped according to the treatment actually received. Safety parameters to be evaluated include adverse events (including deaths, serious adverse events, discontinuations due to adverse events, and the incidence and severity of adverse events), clinical laboratory tests, vital signs, and ECGs. All collected adverse event data will be listed by study site and patient number. All adverse events that occur on or after treatment on Day 1 will be summarized for each treatment group by mapped term, appropriate thesaurus levels, body system, and event within each body system, and toxicity grade. In addition, all serious adverse events, including deaths, will be listed separately and summarized. Serious adverse events caused by a protocol-mandated intervention (e.g., invasive procedures such as biopsies, discontinuation of medications) that occur between consent and first dose of study medication will be listed separately.

Laboratory data with values outside of the normal ranges will be identified. In addition, select laboratory data will be summarized by treatment group using descriptive summary statistics.

The absolute and percentage changes from baseline in vital sign parameters will be computed, and changes deemed clinically significant by the Investigator will be noted. Appropriate descriptive summary statistics will be provided for all vital sign parameters.

The prevalence (baseline) of ATA will be reported and correlation with PK, safety, efficacy, and *biomarker* endpoints will be analyzed as data allow.

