Appendix 3 (cont'd)

DAIDS Toxicity Grading Tables for Clinical Abnormalities

Systemic (General)	Mild (Grade 1)	Moderate (Grade 2)	Severe (Grade 3)	Potentially Life Threatening (Grade 4)
Nausea/vomiting	No interference with activity or 1–2 episodes/24 hours	Some interference with activity or >2 episodes/24 hours	Prevents daily activity, requires outpatient IV hydration	ER visit or hospitalization for hypotensive shock
Diarrhea	2–3 loose stools or <400 g/24 hours	4–5 stools or 400–800 g/24 hours	5 or more watery stools or >800 g/24 hours or requires outpatient IV hydration	ER visit or hospitalization
Headache	No interference with activity	Repeated use of non-narcotic pain reliever >24 hours or some interference with activity	Significant; any use of narcotic pain reliever or prevents daily activity	ER visit or hospitalization
Fatigue	No interference with activity	Some interference with activity	Significant; prevents daily activity	ER visit or hospitalization
Myalgia	No interference with activity	Some interference with activity	Significant; prevents daily activity	ER visit or hospitalization

g=gram; IV=intravenous.

Systemic Illness	Mild (Grade 1)	Moderate (Grade 2)	Severe (Grade 3)	Potentially Life Threatening (Grade 4)
Illness or clinical adverse event (as defined according to applicable regulations)	No interference with activity	Some interference with activity no requiring medical intervention	Prevents daily activity and requires medical intervention	ER visit or hospitalization

Appendix 4

DAIDS Toxicity Grading Tables for Laboratory Abnormalities ^a

HEMATOLOGY				
	Grade 1	Grade 2	Grade 3	Grade 4
Hemoglobin	9.5–10.5 g/dL	8.0–9.4 g/dL	6.5–7.9 g/dL	< 6.5 g/dL
Absolute Neutrophil Count	1,000–1,500/mm ³	750–999/mm ³	500–749/mm ³	< 500/mm ³
*Platelets	125,000–140,000/mm ³	100,000–124,999/mm ³	25,000–99,999/mm ³	< 25,000/mm ³
WBCs	11,000–13,000/mm ³	13,000–15,000/mm ³	15,000–30,000/mm ³	> 30,000 or < 1,000/mm ³
*Lymphocytes Decrease – cell/mm ³	750–1,000	500–749	250–499	< 250
*Eosinophils – cell/mm ³	650–1500	1501–5000	> 5000	Hypereosinophilic
Abnormal Fibrinogen	Low: 100–200 mg/dL High: 400–600 mg/dL	Low: < 100 mg/dL High: > 600 mg/dL	Low: < 50 mg/dL	Fibrinogen associated with gross bleeding or with disseminated coagulation
Fibrin Split Product	20–40 mcg/mL	41–50 mcg/mL	51–60 mcg/mL	> 60 mcg/mL
Prothrombin Time (PT)	1.01–1.25 × ULN	1.26–1.50 × ULN	1.51–3.0 × ULN	> 3 × ULN

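### Section 6.4 plans no laboratory table by toxicity grade or against baseline, so the laboratory part of the graded primary outcome is not delivered

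*Combined protocol and SAP*

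**What the plan says.** Section 3.4.1 makes adverse events and clinical laboratory abnormalities the primary outcome. Both are "graded according to the Division of Acquired Immunodeficiency Syndrome [DAIDS] Toxicity Grading Tables for Clinical Abnormalities" and are to be judged by changes in, among other things, laboratory results. Section 2.1 lists effects on laboratory values within the primary objective. Grade 1 to 4 cut-offs for laboratory tests are in Appendix 4, "DAIDS Toxicity Grading Tables for Laboratory Abnormalities".

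Section 6.4 has two sentences on laboratory data. The first is "Laboratory data with values outside of the normal ranges will be identified". The second is that "select laboratory data will be summarized by treatment group using descriptive summary statistics"; the tests are not named. For adverse events, the same section plans a by-arm summary down to "event within each body system, and toxicity grade". For vital signs it says "The absolute and percentage changes from baseline in vital sign parameters will be computed". Section 6.3 defines baseline as the last value before study drug.

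Section 5.7 lists among anticipated events: "Asymptomatic elevations of ALT, AST, and/or amylase without corresponding elevations of bilirubin have been shown to be increased during influenza A infection".

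**The concern.** The outcome is defined by grade and by change. The laboratory analysis plan commits to neither. If Section 6.4 is followed as written, the report will hold a list of out-of-range values and some descriptive statistics, but not the incidence and severity of graded laboratory abnormalities by arm.

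The disease makes this more than a formality. The protocol says that liver enzymes and amylase rise during influenza A, and patients are dosed up to 72 hours after onset. Some may therefore be out of range before dosing. A flag does not separate them from patients who become abnormal on treatment. It also misses worsening: under Appendix 4, an ALT that goes from 1.5 to 4 times the upper limit moves from grade 1 to grade 3, yet it is flagged both times. These enzymes were the most common treatment-emergent events in the challenge study (Section 1.2.2.3), so they deserve a specified table.

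**Working it through.** **Outcome against analysis.**

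| Component of Section 3.4.1 | Adverse events in 6.4 | Vital signs in 6.4 | Laboratory data in 6.4 |
|---|---|---|---|
| By toxicity grade, by arm | Yes | Not stated | Not stated |
| Against baseline | Events on or after treatment | Absolute and percentage change | Not stated |

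The graded adverse-event table does not close the gap. Under Section 5.3.5.5 a laboratory result must be reported as an adverse event only if a repeat confirms it and it also has symptoms, changes treatment, leads to an intervention, or is judged clinically significant. That table therefore holds a filtered subset of laboratory abnormalities.

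**The plan's own figures.** The plan gives none for the laboratory comparison. Table 5 (exact binomial, 40 per arm) reproduces: at a true rate of 5%, 87.2% for at least one event and 60.1% for at least two, against the stated 87% and 60%. Nothing below changes Table 5 or the 141 patients.

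**Illustration of the noise.** From the documents: 47 per arm (Section 6.1). Assumed, because the documents give no values: a share b abnormal at baseline, who stay flagged, and new-elevation rates e of 5% on placebo and 15% on active among patients normal at baseline. All 47 patients are the denominator for both counts.

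- Any out-of-range value: p = b + (1 − b)e
- New (treatment-emergent) abnormality: q = (1 − b)e
- SE = √[(p₀(1 − p₀) + p₁(1 − p₁))/47], and likewise with q; z = difference/SE

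For b = 0.2:

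- Out of range: 0.2 + 0.8 × 0.05 = 24% and 0.2 + 0.8 × 0.15 = 32%. SE = √[(0.1824 + 0.2176)/47] = 0.0923; z = 0.08/0.0923 = 0.87.
- New: 0.8 × 0.05 = 4% and 0.8 × 0.15 = 12%. SE = √[(0.0384 + 0.1056)/47] = 0.0554; z = 0.08/0.0554 = 1.45.

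| b | Out of range, placebo vs active | New, placebo vs active | Difference, either count | z, out of range | z, new |
|---|---|---|---|---|---|
| 0 | 5% vs 15% | 5% vs 15% | 10 points | 1.64 | 1.64 |
| 0.2 | 24% vs 32% | 4% vs 12% | 8 points | 0.87 | 1.45 |
| 0.3 | 33.5% vs 40.5% | 3.5% vs 10.5% | 7 points | 0.70 | 1.34 |
| 0.4 | 43% vs 49% | 3% vs 9% | 6 points | 0.58 | 1.23 |

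The difference is the same in both columns because b cancels. Only the standard error changes. For b = 0.2 the 95% half-width is 1.96 × 0.0923 = 18.1 points against 1.96 × 0.0554 = 10.8 points. The ratio of z values is 0.87/1.45 = 0.60 at b = 0.2 and 0.58/1.23 = 0.47 at b = 0.4, a loss of about 40% to 53%.

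**Sensitivity to background.** With b = 0.2 and assumed new-elevation rates of 37.5% versus 47.5%:

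- Out of range: 50% vs 58%; SE = √[(0.25 + 0.2436)/47] = 0.1025; z = 0.78.
- New: 30% vs 38%; SE = √[(0.21 + 0.2356)/47] = 0.0974; z = 0.82.

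The gain nearly vanishes when many rises first appear after dosing.

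**The case against.** Much of the safety reporting is in place. All adverse events on or after treatment are summarised by arm and toxicity grade, including laboratory abnormalities reported as events. Section 5.3.5.7 requires reporting of raised ALT or AST combined with raised bilirubin or jaundice. By-arm descriptive statistics are planned for some tests, and nothing in that wording forbids shift tables. The IMC and SOC review unblinded data (Section 3.1.3) and watch the anticipated enzyme rises for imbalance (Section 5.7). Section 4.1.2 excludes patients with laboratory abnormalities that the investigator deems clinically significant.

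These points limit the gap to laboratory grades that never become adverse events. They do not close it: permission is not a commitment, committee monitoring is not the specified primary analysis, and the exclusion leaves room for mild elevations at entry.

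A reader might also infer four stronger points that the documents do not support.

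- That influenza's own elevations swamp a drug effect. They are expected equally in all arms, so they add noise and no bias.
- That many patients will be out of range before dosing. No pre-dose rate is given. In the challenge study the enzyme elevations were post-dose events (15 events in 40 control subjects, 26 in 60 given MHAA4549A), and these counts are not shares of patients.
- That flagging shrinks a 10-point difference to 8 or 6. That compares a rate among patients normal at baseline with a rate among all patients. On one denominator the differences are equal. A 10-point difference would need patients already abnormal to worsen at 5% versus 15% too, which nothing supports.
- That the graded primary outcome is missing altogether. Only its laboratory part is.

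**Conclusion.** The point holds for the laboratory part of the primary outcome. Section 6.4 commits to no summary of laboratory values by Appendix 4 grade and to no comparison with baseline, while Section 3.4.1 defines the outcome by both. This follows from the text and needs no assumption.

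The statistical cost is lost precision, not bias, and its size is unknown. Under the assumed 20% to 40% abnormal at baseline, with 5% versus 15% new elevations and 47 per arm, z falls from 1.45 to 0.87 at the low end and from 1.23 to 0.58 at the high end. The loss is zero if nobody is abnormal at baseline and small if post-dose background rises are common. Because Section 6 plans no formal hypothesis testing, z is only a yardstick. The calculation also counts a baseline-abnormal patient as flagged whatever happens later, since Section 6.4 does not say how the flags are to be counted.

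This is a free improvement. No sample-size or error-rate figure changes.

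**What to change.** In Section 6.4, tabulate by arm, for each analyte, the worst post-baseline Appendix 4 grade against the baseline grade. Report the proportion worsening by at least one grade, with the difference from placebo and its 95% confidence interval for each dose. Name the tests that get descriptive statistics.

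Apply this to every Table 2 analyte that has an Appendix 4 grade and scheduled post-dose samples, that is, within hematology, chemistry and urinalysis. Appendix 1 schedules these at screening, Day 3 and Day 7. Leave out PT and aPTT: the main schedule has the coagulation panel on Day 1 only, with Day 1 assessments before dosing, so no shift can be formed outside the recurrent-influenza schedule. Lipase is measured only when amylase is above the upper limit, so it is better listed.

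Also point Section 3.4.1 to Appendix 4 for laboratory grades, because it now cites the tables for clinical abnormalities.

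Shift tables remove only what was present at baseline. Influenza-driven rises that first appear after dosing still count as new, and the comparison with placebo handles them. The cost is a few standard tables from data already collected.

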6.5 SECONDARY EFFICACY ANALYSES

The efficacy analyses will include all randomized patients who are confirmed to be influenza A infected, with patients grouped according to the treatment assigned at randomization. Efficacy parameters to be evaluated include duration and severity of influenza symptoms, hospitalization, and influenza-related complications.

Time to event data will be analyzed using Kaplan-Meier methodology and will be summarized using n, median when estimable, hazard ratios, and 95% confidence intervals. Patients who are lost to follow-up (while event free) will be censored at the time that they are last known to be event free.

Estimation of the treatment difference of proportions and its 95% confidence interval will be calculated using stratum-adjusted Mantel-Haenszel methodology ([Koch et al. 1989](#)). For continuous endpoints, Analysis of Covariance methods (after appropriate transformation of data) will be used to estimate treatment differences and 95% confidence intervals.

Other than censoring in the time to event analyses, no other imputation for missing data will be performed.

6.5.1 Secondary Endpoints

- Median time to alleviation of clinical signs and symptoms of influenza A infection
- Proportion of patients requiring hospitalization
- Median duration of hospitalization
- Proportion of patients with influenza-related deaths
- Proportion of patients requiring antibiotics for respiratory infection
- Proportion of patients with influenza secondary complications
- Proportion of patients with influenza re-infection

6.5.2 Exploratory Endpoints

- 

[REDACTED]

[REDACTED]

[REDACTED]

[REDACTED]

[REDACTED]

[REDACTED]

[REDACTED]

[REDACTED]

[REDACTED]

[REDACTED]

[REDACTED]

6.6 SUBGROUP ANALYSES

Subgroup analyses will be performed to examine the consistency of the treatment estimates with use of the endpoints. Subgroups will include the stratification factors. Additional subgroups may be added following assessment of baseline characteristics as exploratory analyses.

6.7 PHARMACOKINETIC ANALYSES

Individual and mean serum MHAA4549A concentration versus time data will be tabulated and plotted. The serum PK of MHAA4549A will be summarized by estimating total serum drug exposure (i.e., AUC), *maximum* concentration (C_{max}), total serum clearance, half-life, and volume of distribution, as data allow. Estimates for these parameters will be tabulated and summarized (e.g., mean, standard deviation, coefficient of variation). Inter-patient variability will be evaluated. MHAA4549A serum concentration-time data may be compared with available data from other MHAA4549A clinical studies.

Additional PK analyses, such as population PK, may be conducted as appropriate and reported separately. Potential correlations between relevant PK parameters and safety or efficacy outcomes, as well as other covariates, may also be explored and reported separately.

6.8 EXPLORATORY ANALYSES

[REDACTED]

[REDACTED]

[REDACTED]

[REDACTED]

[REDACTED]

6.8.1 Biomarker Analyses

[REDACTED]

[REDACTED]

6.9 IMMUNOGENICITY ANALYSES

The immunogenicity analyses will be limited to testing of predose samples from all patients enrolled in the study. No post-dose samples will be collected (except for Day 7 in the case of recurrent influenza).

The number of ATA-positive patients at baseline will be determined, which will provide an estimate of the prevalence of pre-existing ATAs in this patient population.

[REDACTED]

No additional immunogenicity assessments are planned for this study.

6.10 INTERIM ANALYSES

6.10.1 Optional Interim Analyses

Given the hypothesis-generating nature of this study, the Sponsor may choose to conduct up to two interim efficacy analyses. The decision to conduct an optional interim analysis and the timing of the analysis will be documented in the Sponsor's trial master file prior to the conduct of the interim analysis. The interim analysis will be performed and interpreted by members of the Sponsor study team and appropriate senior management personnel who will be unblinded at the treatment group level. Access to treatment assignment information will follow the Sponsor's standard procedures. If

conducted, an interim analysis would be for administrative purposes only (i.e., internal planning or decision making) and would not impact the conduct of the current study in any way. A nominal type 1 error penalty of 0.0001 will be taken.

7. DATA COLLECTION AND MANAGEMENT

7.1 DATA QUALITY ASSURANCE

The Sponsor will be responsible for data management of this study, including quality checking of the data. Data entered manually will be collected via EDC through use of eCRFs. Sites will be responsible for data entry into the EDC system. In the event of discrepant data, the Sponsor will request data clarification from the sites, which the sites will resolve electronically in the EDC system.

The Sponsor will produce an EDC Study Specification document that describes the quality checking to be performed on the data. Central laboratory data will be sent directly to the Sponsor, using the Sponsor's standard procedures to handle and process the electronic transfer of these data.

eCRFs and correction documentation will be maintained in the EDC system's audit trail. System backups for data stored by the Sponsor and records retention for the study data will be consistent with the Sponsor's standard procedures.

Data from paper diaries will be entered into the EDC system by site staff.

7.2 ELECTRONIC CASE REPORT FORMS

eCRFs are to be completed through use of a Sponsor-designated EDC system. Sites will receive training and have access to a manual for appropriate eCRF completion. eCRFs will be submitted electronically to the Sponsor and should be handled in accordance with instructions from the Sponsor.

All eCRFs should be completed by designated, trained site staff. eCRFs should be reviewed and electronically signed and dated by the investigator or a designee.

At the end of the study, the investigator will receive patient data for his or her site in a readable format on a compact disc that must be kept with the study records. Acknowledgement of receipt of the compact disc is required.

7.3 PATIENT-REPORTED DAILY SYMPTOM DATA

Data from paper diaries will be entered into the EDC system by site staff.

7.4 SOURCE DATA DOCUMENTATION

Study monitors will perform ongoing source data verification to confirm that critical protocol data (i.e., source data) entered into the eCRFs by authorized site personnel are accurate, complete, and verifiable from source documents.

Source documents (paper or electronic) are those in which patient data are recorded and documented for the first time. They include, but are not limited to, hospital records, clinical and office charts, laboratory notes, memoranda, patient-reported outcomes, evaluation checklists, pharmacy dispensing records, recorded data from automated instruments, copies of transcriptions that are certified after verification as being accurate and complete, microfiche, photographic negatives, microfilm or magnetic media, X-rays, patient files, and records kept at pharmacies, laboratories, and medico-technical departments involved in a clinical trial.

Before study initiation, the types of source documents that are to be generated will be clearly defined in the Trial Monitoring Plan. This includes any protocol data to be entered directly into the eCRFs (i.e., no prior written or electronic record of the data) and considered source data.

Source documents that are required to verify the validity and completeness of data entered into the eCRFs must not be obliterated or destroyed and must be retained per the policy for retention of records described in Section 7.6.

To facilitate source data verification, the investigators and institutions must provide the Sponsor direct access to applicable source documents and reports for trial-related monitoring, Sponsor audits, and IRB/EC review. The study site must also allow inspection by applicable health authorities.

7.5 USE OF COMPUTERIZED SYSTEMS

When clinical observations are entered directly into a study site's computerized medical record system (i.e., in lieu of original hardcopy records), the electronic record can serve as the source document if the system has been validated in accordance with health authority requirements pertaining to computerized systems used in clinical research. An acceptable computerized data collection system allows preservation of the original entry of data. If original data are modified, the system should maintain a viewable audit trail that shows the original data as well as the reason for the change, name of the person making the change, and date of the change.

7.6 RETENTION OF RECORDS

Records and documents pertaining to the conduct of this study and the distribution of IMP, including eCRFs, paper diaries, Informed Consent Forms, laboratory test results, and medication inventory records, must be retained by the Principal Investigator for at least 15 years after completion or discontinuation of the study, or for the length of time required by relevant national or local health authorities, whichever is longer. After that period of time, the documents may be destroyed, subject to local regulations.

No records may be disposed of without the written approval of the Sponsor. Written notification should be provided to the Sponsor prior to transferring any records to another party or moving them to another location.

8. ETHICAL CONSIDERATIONS

8.1 COMPLIANCE WITH LAWS AND REGULATIONS

This study will be conducted in full conformance with the ICH E6 guideline for Good Clinical Practice and the principles of the Declaration of Helsinki, or the laws and regulations of the country in which the research is conducted, whichever affords the greater protection to the individual. The study will comply with the requirements of the ICH E2A guideline (Clinical Safety Data Management: Definitions and Standards for Expedited Reporting). Studies conducted in the United States or under a U.S. Investigational New Drug (IND) application will comply with U.S. FDA regulations and applicable local, state, and federal laws. Studies conducted in the European Union (E.U.) or European Economic Area will comply with the E.U. Clinical Trial Directive (2001/20/EC).

